# 6 Study design

This proposed project has 3-stages (see above study schema on page 14):

Stage 1: Development of training materials and an intervention manual for ASSIST+Frank and Frank friends;

Stage 2: Piloting of ASSIST+Frank in one school and Frank friends in one school followed by a period of refinement of the interventions;

Stage 3: Exploratory 4-arm trial with cluster randomisation (at the level of school) in 12 state secondary schools in South Wales with an embedded process evaluation.

# 7 School and participant selection

Schools and participants are eligible for the trial if they meet all of the following inclusion criteria and none of the exclusion criteria. All queries about school eligibility should be directed to the ASSIST+Frank Study Manager ([name]) before randomisation.

#### 7.1 Inclusion criteria

Schools will be recruited and randomised if they are among the state secondary schools identified by Welsh Government and Public Health Wales as eligible to receive the ASSIST intervention in academic year 2013-2014. Students in year 8 in these schools in 2013-2014 will be eligible participants in baseline and follow-up data collections (baseline conducted in year 8; 18-month follow-up year 9).

### 8 Outcome measures

The primary aim of the exploratory trial will be to assess the feasibility and acceptability of delivering the ASSIST+Frank and Frank friends interventions as well as trial methods prior to a phase III definitive trial.

# 8.1 Progression criteria

Within the exploratory trial, a process evaluation will inform assessment against the following progression criteria (to be agreed in advance by the Trial Steering Committee):

Acceptability and feasibility of the interventions to school and intervention delivery staff

- 1. Was it feasible to implement the ASSIST+Frank intervention in (at least) 2 out of 3 intervention schools? This will be assessed according to whether: a) 75%+ of year 8 ASSIST peer supporters are recruited and re-trained as ASSIST+Frank peer supporters in year 9; b) 75%+ of year 9 students nominated are recruited and trained as Frank friends peer supporters and, c) PHW staff delivered the additional ASSIST+Frank training in full in all 3 intervention schools. This will be assessed via interviews and focus groups with peer supporters and PHW staff, as well as observations of peer supporter training.
- 2. Was it feasible to implement the Frank friends intervention in (at least) 2 out of 3 intervention schools? This will be assessed according to whether: a) PHW staff delivered the Frank friends training in full in all 3 schools. This will be assessed via interviews and focus groups with peer supporters and PHW staff, as well as observations of peer supporter training.

Acceptability of the intervention to peer supporters and fidelity

- 3. Was the intervention acceptable to students trained as ASSIST+Frank peer supporters? This will be assessed according to whether: a) 75%+ of ASSIST+Frank peer supporters report having at least 1 or more informal conversations with their peers at school about drug-related risks/harms; and b) 75%+ of ASSIST+Frank peer supporters report at least one contact with PHW staff, either via a follow-up visit and/or contact via email, text or Facebook. This will be assessed via interviews and focus groups with peer supporters and PHW staff, and analysis of documentary evidence (e.g. PHW log of attendance at follow-ups, etc.).
- 4. Was the intervention acceptable to students trained as Frank friends peer supporters? This will be assessed according to whether: a) 75%+ of Frank friends peer supporters report having at least 1 or more informal conversations with their peers at school about drug-related risks/harms; and b) 75%+ of Frank friends peer supporters report on-going contact with PHW staff throughout the year via a follow-up visit. This will

be assessed via interviews and focus groups with peer supporters and PHW staff, and analysis of documentary evidence (e.g. PHW log of attendance at follow-ups, etc.).

Acceptability of the intervention to school staff and parents

- 5. Was the ASSIST+Frank intervention acceptable to the majority of school senior management teams (SMT), other school staff, and parents? This will be assessed via interviews with SMT and focus groups with school staff and parents.
- 6. Was the Frank friends intervention acceptable to the majority of school senior management teams (SMT), other school staff, and parents? This will be assessed via interviews with SMT and focus groups with school staff and parents.

Acceptability of the trial design and assessment methods

7. Were the trial design and methods acceptable and feasible? This will be assessed according to whether: a) randomization occurred as planned and was acceptable to SMTs; b) a minimum of 5 out of 6 intervention schools and 2 out of 3 schools from the comparison arms participate up in the 18 month follow-up? and, c) the student survey response rates are acceptable at baseline (80%+) and follow-up (75%+).

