#### 9.6 Randomisation

In the exploratory trial, randomisation of schools will occur after all schools have completed baseline data collection. Schools will be randomly assigned to one of the 4 arms with an assignment ratio of 3: 3: 3: 3. Allocation will be conducted by an independent SEWTU statistician, blind to the identity of schools, and minimised on: the percentage of pupils in receipt of free school meals and school size to balance the randomisation. Optimal allocation will be used to carry out the randomisation. Here a balance algorithm is used when predefined sequence generation is required or when all units are randomised jointly. Data on school size and free school meal entitlement will be collected at recruitment and used to balance the randomisation.

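### Section 8.1 counts Frank friends recruitment under ASSIST+Frank, gives Frank friends no recruitment threshold of its own, and sets conflicting school-level pass marks

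*Protocol*

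**What the plan says.** Protocol section 8.1 sets out seven progression criteria, to be agreed in advance by the Trial Steering Committee (TSC) and informed by the process evaluation.

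Item 1 concerns the adjunct: "Was it feasible to implement the ASSIST+Frank intervention in (at least) 2 out of 3 intervention schools". It has three tests:
- (a) "75%+ of year 8 ASSIST peer supporters are recruited and re-trained as ASSIST+Frank peer supporters in year 9";
- (b) the Frank friends recruitment and training test: "b) 75%+ of year 9 students nominated are recruited and trained as Frank friends peer supporters";
- (c) "PHW staff delivered the additional ASSIST+Frank training in full in all 3 intervention schools".

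Item 2 concerns the stand-alone intervention: "Was it feasible to implement the Frank friends intervention in (at least) 2 out of 3 intervention schools". It has one test, still lettered as the first of a list: "a) PHW staff delivered the Frank friends training in full in all 3 schools".

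The two interventions are separate trial arms with three schools each. Section 9.6 states: "Schools will be randomly assigned to one of the 4 arms with an assignment ratio of 3: 3: 3: 3".

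**The concern.** The trial's primary aim (section 5.1) is to judge feasibility and acceptability in order to decide on a full-scale trial. Sections 14.1 and 15.1 say that the study is not powered for effect and that no p-values will be presented. The progression criteria therefore carry much of the decision, and the summary in section 3.3 says each intervention will be assessed against them. Three features of items 1 and 2 stop them doing this cleanly.

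- A Frank friends measure sits under the ASSIST+Frank question.
- The Frank friends question has no recruitment threshold.
- The school-level pass mark in the question differs from the one in the delivery test beneath it.

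The result could be a verdict on one intervention that reflects what happened in the other's schools, or a verdict that the text leaves undetermined and that is settled only once results are known.

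**Working it through.** The protocol derives no figure for these criteria, so there is none to reproduce. The first three steps compare the text; the last two give a scale.

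**Step 1: which arm does test 1(b) describe?** Under section 11.1.2, ASSIST+Frank re-engages students who were ASSIST supporters in year 8 and holds no new nomination. Under section 11.1.3, Frank friends begins with a year 9 nomination, and the 17.5% with most nominations are invited. Test 1(b) is a proportion of year 9 nominees, so it can only be measured in the three Frank friends schools. It carries no information on the three ASSIST+Frank schools.

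**Step 2: is Frank friends recruitment tested elsewhere?**
- Item 2: delivery of training only.
- Criterion 4: percentages of students already trained as Frank friends supporters, so a recruitment shortfall does not show.
- Criterion 6: acceptability to senior management, other staff and parents.
- Criterion 7: randomisation, school retention and survey response.

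None sets a recruitment threshold for Frank friends. The 75% figure exists in section 8.1, but under the ASSIST+Frank item.

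**Step 3: the pass marks, by number of schools with full delivery.**

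| Schools with full delivery | Item 2 question (at least 2 of 3) | Item 2 only test (all 3) |
|---|---|---|
| 3 | met | met |
| 2 | met | failed |
| 0 or 1 | failed | failed |

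The two agree except at exactly 2. Item 1 gives the same table for test (c) against its question, unless 2 of 3 is taken to govern only (a) and (b).

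**Step 4: how often would exactly 2 occur?** The documents give no per-school probability of full delivery, p. Assume values from 0.70 to 0.95 and independent schools. Then:
- P(at least 2 of 3) = 3p²(1 − p) + p³
- P(all 3) = p³
- P(exactly 2) = 3p²(1 − p), the difference between them

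| p (assumed) | At least 2 of 3 | All 3 | Exactly 2 |
|---|---|---|---|
| 0.70 | 0.784 | 0.343 | 0.441 |
| 0.80 | 0.896 | 0.512 | 0.384 |
| 0.90 | 0.972 | 0.729 | 0.243 |
| 0.95 | 0.993 | 0.857 | about 0.135 |

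For example, at p = 0.80: 3 × 0.64 × 0.20 = 0.384.

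**Step 5: the 75% threshold.** With 150 to 170 students per year group (section 14.1), 17.5% is 26.25 to 29.75 nominees per school. Over three schools that is 78.75 to 89.25, and 75% of these is about 59 to 67 trained supporters. Item 1 does not say whether 75% applies in each school or to the arm as a whole, and the two differ. With equal school sizes, a pooled 75% is reached with two schools at 100% and the third at 25%, since (100 + 100 + 25)/3 = 75.

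**The case against.** The strongest reply is that this is a drafting slip in provisional criteria. The Frank friends threshold is in section 8.1, it names Frank friends, and item 2's lone lettered test suggests that a clause was misplaced. A TSC reading the whole section would probably see this. It stands as an explanation of the error, but agreement by the TSC does not itself correct the wording, and the TSC might adopt the text as it is.

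A reader might infer that low Frank friends recruitment automatically fails ASSIST+Frank. The documents do not go that far. The process evaluation informs an assessment, the tests are what feasibility is assessed according to, and no sentence says that missing one test fails the item. The supported statement is that a shortfall counts against the wrong intervention.

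A reader might also infer that Frank friends passes item 2 however few supporters it recruits, down to none. That is wrong at the low end: the item requires "PHW staff delivered the Frank friends training in full in all 3 schools", which needs students to train in each school. What is missing is a numerical threshold.

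In item 1, 2 of 3 could govern the two recruitment tests and all 3 only the trainers' delivery. This is possible but unstated, and it cannot rescue item 2, where the delivery test is the only one.

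Finally, the binomial figures rest on assumed probabilities and independence. Sections 11.1.2 and 11.1.3 assign training to the same Public Health Wales team, so failures may be correlated across schools. Positive correlation lowers the chance of exactly 2 in this range, and perfect correlation makes it zero. This objection stands against the size, not against the contradiction.

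**Conclusion.** Items 1 and 2 are wrong as written. The misplacement of 1(b) and the absence of a numerical recruitment threshold in item 2 follow from the text alone and need no assumption. So does the pass-mark conflict in item 2. In item 1 that conflict is arguable, because one unstated reading would remove it.

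The 44% to 14% range for a split result is illustrative. It concerns only the delivery test, not the chance of passing the whole of item 1, and it depends on the assumed p and on independent schools.

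No outcome, randomisation step or data collection is affected, and criteria 3 to 7 are untouched. The point still needs correcting, because these items are stated decision rules for the primary aim and must be clear before results are known.

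**What to change.** 1. Move 1(b) to item 2 as the Frank friends recruitment test.
2. In each item, state one school-level pass mark, or say explicitly which tests 2 of 3 governs and which all 3 governs. The choice is for the sponsor and the TSC.
3. State whether each 75% threshold applies per school or pooled over the arm. A rule that 2 of 3 schools must meet every test only works if it is per school.
4. State that each intervention is scored only on its own three schools.
5. Record the TSC's agreement before year 9 delivery begins.

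The cost is a wording change and one TSC decision. No new data are needed.

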We will collect detailed information on social networks to map contacts between peer supporters and drug and non-drug using peers. We will collect data on: up to five best friends inside or outside school, boyfriends/ girlfriends; and explore changes in: the average level of drug use amongst school friends, drug use amongst peer-leaders and their peer groups, isolated students (with no nominations), and the number of friends in and outside of school, as well as the number of nominations sent and received. We will also collect data on the frequency of communication with peers on the harms or risks associated with drug use and the method of communication (face to face, the internet (including what websites), instant messaging via smart phone, texting) as responses may inform the design of future interventions.

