#### 11.1.2 ASSIST+Frank

The intervention manual for ASSIST+Frank has yet to be developed and will undergo extensive piloting. There may therefore be revisions to the outline below. At present it is anticipated that ASSIST+Frank will have four stages:

- Reengagement of ASSIST peer supporters: ASSIST year 8 peer supporters will be
  invited in year 9 to continue and extend their role. Trainers will make it clear that
  students who take drugs can only be peer supporters if they commit to reduce and try to
  stop taking any drugs (in line with the ASSIST model);
- 2. Training of peer supporters: ASSIST+Frank peer supporters will revisit key exercises on communication skills including, listening, negotiation, and ways of giving information; new sessions will focus on: the effects and risks associated with specific drugs and minimising potential harms; how to talk with their peer group about drugs including

aspects of confidentiality and the law; how to access Talk to Frank website (www.talktofrank.com), by smartphone, or by text; and time will be devoted to answering questions. Training will be one full day on drug education and practising conversations and be delivered by the PHW ASSIST team who are experienced in youth work and health-promotion;

- 3. Intervention period: Peer supporters will be asked to have conversations with their peers on the risks of different drugs and log these interactions over 10-weeks. One follow-up visit will be made by two ASSIST+Frank trainers with further contact via by a preferred method (email, text and/or Facebook) when Talk to Frank is updated.
- 4. Acknowledgment of peer supporters' contribution: At the end of the intervention, supporters would receive a certificate with an additional gift voucher for those who handed in their diary.

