#### 11.1.3 Frank friends

The intervention manual for Frank friends has yet to be developed and will undergo extensive piloting. At present it is anticipated that Frank friends will have five stages:

- 1. Nomination of peer supporters: Students aged 13–14 years (UK year 9) are asked to identify influential peers using three questions, "Who do you respect in year 9 at your school?", "Who are good leaders in sports or other groups activities in year 9 at your school?", and "Who do you look up to in year 9 at your school?" The 17.5% of year 9 pupils receiving the most peer nominations are invited to a recruitment meeting;
- Recruitment of peer supporters: A meeting is held with nominees to explain the role of a
  peer supporter and answer questions. Trainers make it clear that students who take drugs
  could only be peer supporters if they commit to reduce and try to stop taking any drugs;
- 3. Training of peer supporters: The aims of the training are to: provide information about the effects and risks associated with specific drugs and minimising potential harms; including the legal consequences; develop communication skills including, listening, cooperation and negotiation, and conflict resolution; enhance students' confidence, empathy, assertiveness, attitudes to risk-taking, and exploration of personal values. The trainers will also discuss the tobacco and alcohol use within this context. Training will be over 2 days on drug education and practising peer supporter skills by the PHW ASSIST team who are experienced in youth work and health-promotion.
- 4. Intervention period: 10-week peer-led intervention where supporters have informal conversations with their peers on the harms associated with different drugs, when

travelling to and from school, in breaks, at lunchtime, and after school in their free time, and log a record of these conversations in a pro-forma diary. Four follow-up school visits

by trainers to meet with peer supporters;

5. Acknowledgment of peer supporters' contribution: All peer supporters are presented with

a certificate; those who hand in their diary are also presented with a gift certificate.

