### 15.3 Qualitative analysis

We will aim for a maximum variation sample to achieve a broad perspective on the issues. The sampling criteria will be: school, trial arm, participant type (teacher, peer-supporter, pupil, parent) and gender. Emergent issues from earlier interviews and focus groups will be explored in subsequent interviews. We anticipate that 55 interviews will be undertaken, although this will depend on the depth and detail of information provided. All interviews will be recorded and transcribed verbatim. Analysis will be conducted using a structured thematic approach to systematically code, classify and organise interview content into key themes. Broad themes will then be broken down to identify commonly expressed themes and unusual cases. 10% of the data will be coded by two team members to check that the coding scheme is identifying all of the themes and concepts, and that there is a shared understanding of what

they are. Analysis will be conducted using QSR NVivo 10 software to assist systematic coding to identify emerging patterns between teachers, peer-supporters, pupils, parents and schools.

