#### 21 Milestones

[figure not shown]
| M-3-0  | Recruitment of RA and schools;  |
|--------|---|
| M 1-3  | Recruitment of schools; post information sheets and consent forms;                  |
| M 4    | Exploratory trial: baseline data collection   |
| M 5    | Year 8: intervention delivery of ASSIST   |
| M 6    | Input/clean baseline questionnaire data   |
| M 6-7  | Develop intervention materials  |
| M 7-9  | Pilot intervention in two schools, interviews and focus groups                      |
| M10-13 | Input, clean and analyse pilot data; revise interventions                           |
| M14-20 | Year 9: intervention delivery, 10-week follow-up; conduct interviews and focus      |
| M21-22 | 18 month follow-up; final interviews conducted                                      |
| M21-25 | Input/clean questionnaire data; transcription; qualitative and statistical analysis |
| M25-31 | Report writing; dissemination; potential phase III trial application                |

[figure not shown]

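### Progression criterion 4b asks for year-long contact from a 10-week Frank friends programme, so full delivery would not meet it as worded and it has no countable pass rule

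*Protocol*

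**What the plan says.** Protocol section 8.1 lists progression criteria, to be agreed in advance by the TSC. Under section 5.1 the study's primary aim is to decide whether to go on to a full-scale trial, and these criteria serve that decision.

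- Criterion 4b (Frank friends): "75%+ of Frank friends peer supporters report on-going contact with PHW staff throughout the year via a follow-up visit".
- Criterion 3b (ASSIST+Frank): "75%+ of ASSIST+Frank peer supporters report at least one contact with PHW staff, either via a follow-up visit and/or contact via email, text or Facebook".
- Criteria 3a and 4a require 75% or more of supporters to report at least one informal conversation with school peers about drug risks or harms.
- Evidence for criteria 3 and 4: interviews and focus groups with supporters and PHW staff, together with documentary evidence, of which the PHW attendance log is given as an example.

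The programmes are described as follows.

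- Section 11.1.3, Frank friends: a "10-week peer-led intervention where supporters have informal conversations with their peers on the harms associated with different drugs". The same stage lists "Four follow-up school visits".
- Section 11.1.2, ASSIST+Frank: "One follow-up visit will be made by two ASSIST+Frank trainers with further contact via by a preferred method".
- Section 21, months 14 to 20: "Year 9: intervention delivery, 10-week follow-up; conduct interviews and focus" groups.

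On data sources, section 13.3 plans 24 supporter interviews for feasibility and acceptability, a further random sample of 12 supporters in schools with the highest and lowest drug-use incidence, four supporter focus groups, and an analysis of diaries. Section 15.3 says of the qualitative work: "We will aim for a maximum variation sample to achieve a broad perspective on the issues". Section 8.3 adds a questionnaire item: "We will also collect data on the frequency of communication with peers on the harms or risks associated with drug use".

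**The concern.** Criterion 4b tests Frank friends against a contact pattern that its own description does not plan. It also joins an idea of continuity to a single visit and gives no minimum count. Two people holding the same attendance records could therefore reach opposite decisions, and one of those decisions counts against a fully delivered programme.

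A second, smaller matter concerns 3a and 4a. The attendance log shows who met a trainer, not who talked to peers. The protocol names several sources but does not say which one supplies the numerator and denominator of the 75%. If the interviews were used by default, the result would be too imprecise to compare with a threshold.

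**Working it through.** The 75% thresholds are set, not derived, so there is no plan calculation to reproduce for them.

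**1. Criterion 4b against the programme.**

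- Planned contact: four visits, all listed in the 10-week intervention stage (section 11.1.3).
- Share of a calendar year: 10/52 = 0.19.
- Share of a school year of 39 weeks (my assumption): 10/39 = 0.26.
- The whole window in section 21, months 14 to 20, is 7 months (7/12 = 0.58 of a year). It covers delivery in all schools as well as the interviews.

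On none of these figures do the planned visits extend over a year.

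**2. What the ambiguity does to the score.**

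Inputs: 17.5% of the year group invited (section 11.1.3), 170 or alternatively 150 pupils per year group (section 14.1), 3 schools per arm (section 9.6). I assume that every invited pupil is trained.

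- 0.175 × 170 × 3 = 89.25, about 89 supporters. 75% of that is 66.9, so 67 must qualify.
- 0.175 × 150 × 3 = 78.75, about 79 supporters. 75% of that is 59.1, so 59 or 60 must qualify, depending on rounding.

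Take perfect delivery and attendance with 89 supporters:

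| Reading of 4b | Qualify | Result |
|---|---|---|
| At least one follow-up visit | 89 of 89 | pass |
| All four planned visits | 89 of 89 | pass |
| Contact spread over the year | 0 of 89 | fail |

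With imperfect attendance the first two readings would also diverge.

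**3. Criteria 3a and 4a, if interviews alone supplied the percentage.**

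The 24 interviews are not split by arm in the protocol. I assume 12 per intervention and treat them as a simple random sample, which is generous to a maximum-variation sample. Intervals are Clopper-Pearson. Pass probabilities are binomial, P(X ≥ k), where k is the smallest count reaching 75%.

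| Supporters | k | 95% CI at k | Pass if true rate 60% | 65% | 75% | 85% |
|---|---|---|---|---|---|---|
| 12 | 9 | 43–95% | 0.23 | 0.35 | 0.65 | 0.91 |
| 18 | 14 | 52–94% | 0.09 | 0.19 | 0.52 | 0.88 |
| 89 | 67 | 65–84% | 0.002 | 0.025 | 0.53 | 0.995 |

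The row for 18 adds the 12 random-sample interviews, again with an equal split assumed. The row for 89 treats the supporters as a sample from a wider population; for the arm itself it would be a full count. All rows assume independence, and clustering within schools would widen the intervals.

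**4. Should non-responders count as failures?**

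The synopsis expects 80% response, and criterion 7c accepts 75% at follow-up. With response r, the share of responding supporters who must report a conversation is 0.75/r.

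- r = 0.80: 0.75/0.80 = 0.94.
- r = 0.75: 0.75/0.75 = 1.00.

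An acceptable survey return would put the criterion nearly or wholly out of reach, so that rule is unsuitable.

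**The case against.** A reader might infer that the 75% thresholds rest mainly on a small purposive interview sample. The documents do not support that. Section 8.1 names documentary evidence, including the attendance log, for both criteria. Section 13.3 adds diary analysis with no stated sample limit, and one set of 12 interviews is random, though in schools selected by drug-use incidence. The figures for 12 supporters describe only what would follow if interviews alone were scored. What remains is that no source is designated for 3a and 4a, and that the log cannot serve for them.

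A reader might also infer that the two interventions are held to unfairly different standards. Much of the difference between 3b and 4b follows from design: ASSIST+Frank plans one visit plus remote contact, Frank friends four visits. Accepting remote contact in the first and asking for visits in the second is consistent with those plans. The year-long wording is not explained by them.

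On 4b itself, the best defence is that its closing words allow it to be met by attending the planned visits. In addition, section 11.1.3 is a provisional outline with the manual still to be written, and it does not expressly exclude later contact. The criteria also await TSC agreement and inform a judgement; they are not an automatic test. All this is fair, and it makes the defect easy to correct. It does not remove it: the lenient reading sets aside the stated duration, and no later contact is described anywhere in the protocol.

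**Conclusion.** The point holds for criterion 4b. As worded it conflicts with section 11.1.3, and on the same perfect attendance it gives 0 of 89 or 89 of 89 depending on the reading. It should be corrected before the TSC agrees the criteria, because it bears directly on whether Frank friends goes forward. The conflict itself rests on no numerical assumption. The count of 89 assumes year groups of 170 and full take-up by those invited.

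For 3a and 4a the conclusion is conditional. The protocol does not say that interviews decide the percentage. If they did, at an assumed 12 per arm, a true rate of 60% would pass with probability 0.23, against 0.002 with about 89 supporters.

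**What to change.** 1. Reconcile 4b with section 11.1.3. Restate it as the proportion of supporters attending at least a stated number of the planned follow-up visits, with that number agreed by the TSC in advance. Score it from the PHW attendance log, with all trained Frank friends supporters as the denominator. This replaces supporters' own report by recorded attendance. Criterion 3b can keep its remote-contact route.
2. For 3a and 4a, name one source that seeks data from every trained supporter: either the diaries or the existing questionnaire item on communication with peers. Report the proportion among responders next to the response rate, and do not count non-responders as failures. Use interviews and focus groups to explain the result.
3. If the questionnaire item is chosen, check that it can be restricted to peers at school and to the period since training, since section 8.3 does not say so.

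The cost is a wording change, TSC agreement and, for the questionnaire, a link from the list of trained supporters to their identification numbers. The drawbacks are recall over the interval between delivery and the 18-month survey, and non-return of diaries. Return is rewarded with a voucher (section 17.6), and those who return a diary may differ from those who do not.
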